administrations. This criterion is necessary to permit selection of the necessary treatment and generalization probe items as described below, and will minimize ceiling effects on the naming probes. Fourth, in order to avoid enrolling into the study participants who have profound naming impairments and are therefore unlikely to benefit from the study treatment (e.g., patients with global aphasia and/or verbal output limited to recurrent stereotypy), all participants must obtain a CAT Naming modality T-score greater than or equal to 40. Finally, we will exclude from participation potential participants with severe motor speech disorder (i.e., apraxia of speech and/or dysarthria). Motor speech diagnosis and severity judgments will be made by study investigators with experience in this area ([name], [name], [name]), based on the following samples of behavior: Connected speech samples (described below); three recorded attempts at laryngeal diadochokinesis at slow, medium, and fast rates; three trials of maximum sustained phonation; and recorded responses to the three subtests of the Apraxia Battery for Adults-2, including Speech Diadochokinesis, Repetition of Words of Increasing Length, and Word Repetition with Repeated Trials. Two judges will independently diagnose and rate the severity of motor speech disorder in each potential participant. A third judge will provide a diagnosis and rating to resolve any disagreements regarding presence or severity of motor-speech disorders. Chart review of PIRATE participants to date suggests that the above additional five criteria would have excluded approximately 20% of the unique veterans served by the program. Thus, out of 72 patients who will be seen in PIRATE over the four-year duration of the project, approximately 58 should be eligible for enrollment in the study. Of these 58 eligible veterans, it is reasonable to expect that at least 50 will enroll in the study and complete the treatment and all study visits (including follow-up visits). This sample size should be sufficient for detecting the relationships between treatment response, psycholinguistic profile, and cognitive performance relevant to Specific Aim 1, and to detect differences relevant to testing the dose-response hypotheses in Specific Aim 2.

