Some participants may also have co-occurring conditions which would prevent them from participation in the imaging arm of the study (claustrophobia; presence of metal in the body). These participants will be enrolled in the study but will not complete imaging procedures. A chart review of PIRATE participants to date indicates that approximately 20% of veterans enrolled in PIRATE may have such exclusionary criteria: roughly 17% report pacemaker or other implanted metal objects or devices incompatible with MR scanning. Thus, the participant sample used to address the neuroanatomical hypotheses proposed under Specific Aim 1 may be smaller than the sample contributing data the other proposed analyses. Under the worst case scenario of no overlap between these imaging-related exclusionary criteria and those described in the preceding paragraph, we expect to obtain a sample size of 40 participants (50 minus 20%) to conduct the proposed imaging-related analyses. As described in section C.3.1.3 below, this sample size should be sufficient to detect the relationships relevant to the neuroanatomical hypotheses.

C.2 Procedures

The schedule of procedures for participants enrolling in the study is summarized in the flowchart in Figure 4. Participants enrolling in the research study will receive a single pre-treatment structural MRI and a battery of cognitive assessments at program entry (see section C.2.3 below). They will also have their performance on standardized measures of naming and other language functions assessed repeatedly throughout the protocol (see section C.2.2 below), and they will receive an intensive dose of a treatment (SFA) designed to target lexical-semantic processes (see section C.2.1 below). Participants' performance on treated and untreated lexical items will be probed three times weekly, to assess acquisition and generalization and to decide when participants will move to a novel set of treatment exemplars.

Half the participants will be randomly assigned to a delayed-treatment condition. The purpose of this condition is to provide an additional measure of experimental control, to ensure that any observed improvements are not due simply to the social contact afforded by the residential component of the treatment program. Previous work [7] has found that simple exposure or engagement in the absence of specific therapy

[figure not shown]

Figure 4: Testing and treatment procedures for study participants

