activities for participants is insufficient to explain their gains in communicative function. However, inclusion of a delayed-treatment condition will help establish this more conclusively for the current study. The specifics of the delayed-treatment condition are given in section C.2.1.

PIRATE involves a single 2-day visit to VAPHS 4-6 weeks prior to entry for a medical clearance exam and an initial comprehensive speech-language evaluation and to initiate treatment planning. During this visit, the CAT and PALPA subtests (for confirmation of aphasia diagnosis and for participant classification and treatment planning) are administered. Accepted candidates return to VAPHS at program entry and reside in residential villas at the H.J. Heinz campus of VAPHS for 4 weeks (or 5 weeks in the delayed-treatment condition). At program entry, a second CAT is administered to participants, and PIRATE candidates enrolling in the research study will be given structural MRI scans and the battery of cognitive assessments described above. Therapy is provided in existing, dedicated PIRATE treatment rooms, also located on the Heinz campus. The treatment schedule is five days a week, approximately 5 hours a day, for a total of 25 hours of therapy each week. As described below, PIRATE participants enrolled in the proposed research will receive treatment five days a week, for 4 hours per day. All therapy will be provided by PIRATE-dedicated licensed clinical providers with multiple years of experience delivering aphasia therapy. Participants return to VAPHS for a single follow-up visit 4-6 weeks after program exit.

C.2.1 Treatment:

Over 85% of PIRATE participants to date have received treatment focused on spoken word production. This is also the unit of language function and the output modality targeted in the majority of treatment-neuroanatomy/neuroimaging studies reviewed in section A.2 above, as well as the majority of treatment-cognitive prediction studies reviewed in section A.2. SFA treatment will be implemented as described by Boyle & Coelho⁸ and Boyle.⁹ At the beginning of a treatment trial, the target picture will be placed in the center of a chart containing the following entries: Group, use, action, properties, location, and association. A treatment trial will proceed through the following steps:

1. The participant is asked to name the picture.

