Treatment will be conducted five days a week (Monday through Friday) across two daily 120-minute intervals, one morning session and one afternoon session, for a total of 4 hours of treatment per day and 20 hours per week. A 20-minute break will be provided within each 120-minute treatment interval and a 120 minute break will be provided between each 120-minute treatment interval. Time in treatment will be recorded in daily logs, as will the number of exposures to each training exemplar, the number of treatment trials, and the number of features (both novel and recurring) generated for each item on a given treatment trial. In addition, participants will be engaged in planned social and recreational activities on the weekends, such as visits to

local sites and events (like a baseball game). These activities will not target or specifically stimulate language function or the skills trained in therapy.

As indicated above, half the participants will be enrolled in treatment immediately upon their arrival at VAPHS, and half will be entered into the delayed-treatment condition. Participants assigned to the delayed-treatment condition will arrive one week prior to treatment initiation. During this week, they will be in residence at the HJ Heinz campus and engage in non-language recreational activities in 2 two-hour sessions per day (the same schedule as will be followed during treatment). These activities will be led by a study staff member experienced in working with stroke survivors. The morning session will consist of recreational activities regularly conducted at the H.J. Heinz campus, listed in Table 6 below:

Billiards	Recreational Hall, H.J. Heinz campus
Physical exercise	Gym, H.J. Heinz campus
Ceramics, other visual arts	Art Studio, H.J. Heinz campus
Puzzles and board games	Recreational Hall, H.J. Heinz campus

Table 6. Non-language-focused recreational activities for participants enrolled in delayed-treatment condition

The afternoon session will consist of either complementary activities drawn from Table 6 or off-site visits to local destinations. While these sessions will afford multiple social contacts and interactions, typical of structured recreational programs, they will not target specific speech and language behaviors. Participants randomized to the delayed treatment group will receive probes (naming and PNT and other assessments [CAT, discourse measures]) on the same schedule as the no-delay group.

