The first analysis will evaluate whether the social contact associated with PIRATE participation results in improved performance on study measures, independent of any actual aphasia treatment. We will use a multivariate mixed model to test whether there are any differences between the immediate-treatment and delayed-treatment groups at the initiation of treatment, and whether there is any group-by-time interaction suggesting a positive effect of the delayed treatment week. The dependent variables will include performance on treated and untreated naming probes and PNT short forms.

If this analysis finds no significant differences between the groups, it will suggest that any observed treatment gains can be attributed to the SFA treatment rather than general effects of the social contact associated with PIRATE. In this case, the two groups will be collapsed for further analysis. In the unexpected event that this analysis finds a significant difference favoring the delayed treatment condition, it will suggest that observed treatment gains should be attributed to the combination of SFA and the socialization inherent in a residential treatment program, rather than to SFA alone. In this case, we will use the data to estimate the size of the socialization effect and statistically control for it in subsequent analyses, where possible.

C.3.1 Psycholinguistic, cognitive, and neuroanatomical predictors of treatment response

The primary dependent variable for analyses relevant to Specific Aim 1 will be the proportion of correctly-named treated stimuli at study exit (post-treatment), minus the proportion of correctly-named treated stimuli at study entry (pre-treatment). This difference score provides the simplest measure of naming treatment response. Supplementary analyses may be carried out using a related dependent variable, the percentage of possible naming improvement^[10]. This is a derived measure which divides the simple pre-post difference score

by the difference between pre-treatment naming performance and ceiling performance (100% accuracy minus observed pre-treatment accuracy). This measure helps correct for observed differences in baseline accuracy.

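### A comparison covering one week of residential contact, with no stated power, is used to attribute four weeks of gain to SFA

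*Combined protocol and SAP*

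**What the plan says.** C.2 sets up the control arm: "Half the participants will be randomly assigned to a delayed-treatment condition". Under C.2.1, "Participants assigned to the delayed-treatment condition will arrive one week prior to treatment initiation". During that week they "engage in non-language recreational activities in 2 two-hour sessions per day (the same schedule as will be followed during treatment").

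Residence lasts much longer than that week. Under C.2, accepted candidates "reside in residential villas at the H.J. Heinz campus of VAPHS for 4 weeks (or 5 weeks in the delayed-treatment condition"). Social contact does not stop when SFA starts: C.2.1 adds that "participants will be engaged in planned social and recreational activities on the weekends".

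C.3 tests for arm differences at treatment initiation and for a group-by-time interaction that would indicate a benefit of the delayed week. There are two branches:

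- If no significant difference is found, the plan says this will suggest that "any observed treatment gains can be attributed to the SFA treatment rather than general effects of the social contact associated with PIRATE", and the arms are collapsed for all later analysis.
- If the difference favours delay, gains are to be attributed to SFA and socialization together, and "we will use the data to estimate the size of the socialization effect and statistically control for it in subsequent analyses", as far as that is possible.

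No power, target effect or significance level is given for this comparison. The Aim 1 primary variable (C.3.1) is the change from study entry to study exit, which is the whole program.

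**The concern.** The arm exists to separate SFA from the effect of living in the program. It observes contact alone for one week and is then used to interpret four weeks of gain. That step needs an assumption about whether a contact effect is complete after a week or keeps building, and the plan states none.

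The non-significant branch is the more serious one. A small weekly effect can be missed by a one-week test and still add up to a material amount over the program. Under the rule as written, none of it is removed. From entry to exit, weeks of SFA and weeks of residence advance together, so an accumulating contact effect would look like the linear dose trend predicted in C.3.2.

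**Working it through.** **Inputs**

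- Contact-only exposure: 1 week (C.2.1). Residence: 4 weeks, or 5 in the delayed arm (C.2).
- Sample: C.1 expects that "at least 50 will enroll in the study and complete the treatment and all study visits". With half allocated to delay, this is about 25 v 25.
- SD: not given for this comparison. As an assumption I use the SDs of improvement that A.1.1 reports for small groups in other treatment studies, 9 and 17 points, and their pooled value √((17² + 9²)/2) = 13.6.
- Two-sided 5% level: assumed, because none is stated.

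**The plan's own figure.** There is none for this comparison. The nearest is the power of 0.82 in C.3.1.1 (12 v 12, 20 points). With SD 17, SE = 17 × √(2/12) = 6.94, 20/6.94 = 2.88, and 2.88 − 1.96 = 0.92, which gives power 0.82. So the upper end of the assumed range matches the plan's own calculation.

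**Step 1: from one week to four.** Let f(t) be the contact effect after t weeks. The ratio f(4)/f(1) is:

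- one-off effect: 1.0
- weekly increments that halve: 1.88
- square-root growth: 2.0
- linear growth: 4.0
- faster than linear (t to the power 1.5): 8.0

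If study entry means arrival, the linear ratio is 5.0 for the delayed arm.

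**Step 2: what the one-week test can see.** SE = SD × √(2/25). The difference detectable with 80% power is (1.96 + 0.84) × SE.

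| SD | SE | 95% half-width | Detectable, 1 week | Same × 4 |
|---|---|---|---|---|
| 9 | 2.55 | 5.0 | 7.1 | 28.5 |
| 13.6 | 3.85 | 7.5 | 10.8 | 43.1 |
| 17 | 4.81 | 9.4 | 13.5 | 53.9 |

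**Step 3: an effect that matters.** C.3.1.1 treats a 20-point difference in treatment effect as clinically meaningful. Under linear growth, 20 points over four weeks is 5 points per week. The power to detect 5 points is 0.50 at SD 9, 0.26 at SD 13.6 and 0.18 at SD 17. For 80% power the SD would have to be about 5/(2.80 × 0.283) = 6.3 points or less.

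**Step 4: where it bites.**

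- Absolute entry-to-exit gain: it contains f(4), which is 20 points in this example. The non-significant branch removes none of it.
- Overall linear trend: a linear contact effect adds its weekly rate to the slope, here 5 points per week.
- Two- v four-week comparison (C.3.2): it contains f(4) − f(2), which is 0 for a one-off effect and 2 × 5 = 10 points if linear. A constant subtracted from both groups cancels.
- One-week contrasts (C.3.2): the mismatch in length does not arise, because a one-week estimate meets a one-week interval.
- Aim 1 group ANOVA, cognitive regressions and lesion mapping: subtracting one constant from every change score leaves these results unchanged.

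**The case against.** The strongest objection is that the plan does not commit to an unscaled subtraction. A reader might infer that the contact effect would be under-corrected fourfold. The documents do not support that. C.3 leaves the method of control open, and a per-week adjustment would remove a linear effect in full. Fourfold is also only the linear case; it is neither the likely value nor an upper limit. This stands, so in the significant branch the fault is an unspecified extrapolation and not a demonstrated under-correction. In that branch the plan also attributes gains to SFA plus socialization, so it would be wrong to say that contact is there relabelled as SFA.

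A reader might also infer that every Aim 1 and Aim 2 result is contaminated. Step 4 shows that this goes too far.

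The plan has other controls that run through treatment. Weekly non-word repetition probes and 40 unrelated untreated items (C.2.1, C.2.2) help, and treatment sets are introduced in sequence. They are partial controls: contact could help naming without helping non-word repetition, SFA may itself generalize to unrelated items, and C.3 does not use them to bound a four-week contact effect.

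The design may also hold more than one week of information. The delayed arm is probed on the same schedule and is one contact week ahead at each treatment week. If contact and SFA effects add, the arm difference after t treatment weeks is f(t+1) − f(t), and summing over t = 0 to 3 gives f(4). That is a fair point about the data. However, C.3 does not state the time range of its interaction term or plan this use.

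Finally, the SDs are borrowed, and a one-week change without treatment may vary less. Step 2 allows for this: power is adequate for 5 points per week only if the SD is about 6 points or below, and the plan gives no figure to show that it is.

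**Conclusion.** The concern holds in this form: a non-significant comparison covering one week of contact, with no stated power, is taken to support attributing gains over four residential weeks to SFA, and the significant branch gives no rule for carrying its estimate beyond one week. Followed as written, the first branch can clear a contact effect that accumulates to a size the plan calls clinically meaningful. In the illustration, that effect would be missed half the time at SD 9 and about four times in five at SD 17.

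These powers rest on 25 per arm, a two-sided 5% level, borrowed SDs and linear growth. If contact acts once and is complete within a week, the ratio is 1 and no extrapolation problem remains. The documents give no basis for choosing between these shapes. The affected results are the absolute gain, the overall linear trend and the two- v four-week comparison. The plan should be changed, and data already being collected are enough to do it.

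**What to change.** In C.3:

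1. Replace the significance rule. Report the one-week contact estimate and its 95% interval in all cases, including when the arms are pooled.
2. Report the four-week gain with the contact effect removed under a one-off assumption (1 times the estimate) and a linear assumption (4 times), labelled as a sensitivity range, with the uncertainty of the estimate carried through. Note that the 4-times line over-corrects a one-off effect by three times the estimate.
3. State which visit counts as study entry in the delayed arm, since exposure is four weeks from treatment start and five from arrival.
4. Word the conclusion as ruling out contact effects of the first residential week only, unless the gain holds across the range in item 2. Present the non-word repetition and unrelated-item probes beside it as supporting evidence.

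The cost is some wording and two more lines in a table, with no new data. The downside is a wider interval and a less favourable attribution claim. Under the assumed SDs, the contact estimate alone contributes a half-width of about 4 × 5.0 = 20 to 4 × 9.4 = 38 points to the 4-times line, so that line may be too imprecise to settle the question.
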